8.1 Definitions of Events

8.1.1 Adverse Events (AEs)

An AE is defined as any untoward medical occurrence, unintended disease or injury, or untoward clinical signs (including abnormal laboratory findings) in participants, users, or other persons, whether or not related to the WavelinQTM EndoAVF System and whether anticipated or unanticipated. This definition includes events related to the procedures involved. For users or other persons, this definition is restricted to events related to the use of the WavelinQTM EndoAVF System.

8.1.2 Serious Adverse Events (SAEs)

Each AE will be assessed to determine whether it is serious or non-serious. (Note: The term serious is not synonymous with severity, which may be used to describe the intensity of an event experienced by the participant or user). An SAE is an AE that led to any of the following:

- Death; or
- Serious deterioration in the health of the participant, users or other persons as defined by one or more of the following:
 - A life-threatening illness or injury; or
 - A permanent impairment of a body structure or a body function including chronic diseases; or
 - In-patient or prolonged existing hospitalization; or
 - Medical or surgical intervention to prevent life-threatening illness or injury or permanent impairment to a body structure or a body function; or
- Fetal distress, fetal death or a congenital abnormality or birth defect including physical or mental impairment.

8.1.3 Adverse Device Effect (ADE)

An ADE is an AE that is considered to be related to the use of the WavelinQTM EndoAVF System. This includes AEs resulting from insufficient or inadequate IFU, operation, or any malfunction of the WavelinQTM EndoAVF System. Additionally, this definition includes any event resulting from use error or from intentional misuse of the WavelinQTM EndoAVF System.

Note that a use error is defined as a user action or a lack of user action while using the medical device that leads to a different result than intended by the manufacturer or expected by the user. User error includes the inability of the user to complete a task. User errors can result from a mismatch between the characteristics of the user, user interface, task or use environment. Users might be aware or unaware that a use error has occurred. An unexpected physiological response of the participant is not by itself considered a use error. A malfunction of a medical device that causes an unexpected result is not considered a use error.

8.1.4 Serious Adverse Device Effect (SADE) or Unanticipated (Serious) Adverse Device Effect (UADE / USADE)

A Serious Adverse Device Effect (SADE) is an ADE that has resulted in any of the consequences that are characteristic of a SAE.

An Unanticipated (Serious) Adverse Device Effect (UADE / USADE) is any (serious) ADE on health or safety or any life-threatening problem or death caused by, or associated with, the WavelinQTM EndoAVF System, which by its nature, incidence, severity, or outcome has not been identified in the IFU and/or current risk assessment, or any other unanticipated serious problem associated with a device that relates to the rights, safety or welfare of participants.

8.2 Severity of Adverse Event

PIs will assess each AE for its severity (intensity) as experienced by the participant or user according to the following criteria:

- **Mild:** Awareness of a sign or symptom that does not interfere with the participant's activity or is transient and is resolved without treatment or additional sequelae.
- **Moderate:** Interferes with the participant's usual activity and / or requires additional intervention and / or treatment and may have additional sequelae.
- **Severe:** Symptom(s) causing severe discomfort to the participant and / or significant impact on the participant's usual activity. Additional intervention and / or treatment is necessary. Additional sequelae occur.

8.3 Relationship of AE to Device(s) / Procedure / AV Access Circuit

PIs will assess each AE for its relationship to the WavelinQTM EndoAVF System, index procedure or the access circuit as follows:

- *Device Related:* AEs directly attributable to the WavelinQTM EndoAVF System used as part of the index procedure.
- Procedure Related: AEs directly attributable to the index procedure.
 - o Wrist Arterial Procedure Access Related: Procedure related AEs directly attributable to wrist arterial access if used during the index procedure.
- AV Access Circuit Related: This category should be restricted to AEs directly associated with the index AV access circuit defined as the continuum from the heart and the arterial inflow through the AV access to the venous outflow back to the heart.

The following categories should be used for assigning the certainty of the relatedness:

- *Definitely Related:* An AE is definitely related if it is obvious, certain or there is little doubt regarding the relationship.
- *Possibly Related:* An AE is possibly related if it is capable of being related but relatively unlikely or there is insufficient information to determine if the AE is related to the device or procedure.
- Not Related: An AE is not related if it is determined that there is no plausible association.

8.4 Reporting of Events

All AEs should be promptly recorded on the appropriate eCRF (including information on the date of the AE, treatment, resolution, and assessment of relatedness). The clinical course of the AE will be followed according to accepted SOC until the event resolves, stabilizes, or in the opinion of the PI, is no longer considered clinically significant. The PI must supply the Sponsor with information concerning the follow up and / or resolution of the AE. The additional reporting requirements for device- / procedure-related AEs / SAEs or UADEs / USADEs are as follows:

- Device- / procedure-related AEs / SAEs, as well as ADEs / SADEs or UADEs / USADEs must be reported to Sponsor within one (1) working day of the site becoming aware of the event(s).
 - De-identified copies of all relevant documentation (i.e., procedure reports, physician / nurses' notes, discharge summary, etc.) should be submitted to

the Sponsor within 72 hours of knowledge of a UADE or death, as appropriate.

- It is the responsibility of the PI to notify the IRB / EC of applicable AEs in accordance with the governing IRB / EC requirements and / or regulatory authorities according to the local regulations in each participating country.
- UADEs / USADEs will be evaluated and assessed / escalated by the Sponsor per ISO 14155:2020(E) and as per local regulations.

8.4.1 Non-Reportable AEs

Pre-existing conditions should be considered as part of the participant's medical history and should not be reported as an AE unless there is a substantial increase in severity or frequency of the condition, which has not been attributed to natural history. Exacerbation of an existing condition should be reported as an AE if the event meets the CIP definition of an AE.

Planned hospital visits and / or hospital stays, or procedures required by this CIP (including subsequent interventions assessed in the clinical investigation endpoints), without serious deterioration in health should not be considered SAEs.

8.5 Participant Death

Participant death, for any reason during the clinical investigation, must be reported to the Sponsor within one (1) working day of the investigational site becoming aware of the event.

Notification of death must include a brief statement of the pertinent details. All available medical records related to the participant's death must be maintained.

8.6 Device Deficiencies

A device deficiency is any inadequacy of a medical device with respects to its identity, quality, durability, reliability, usability, safety, or performance. Device deficiencies include malfunctions, use errors, and inadequacy in the information supplied by the manufacturer including labeling. A device malfunction is defined as a failure of a medical device to perform in accordance with its intended purpose when used in accordance with the IFU or CIP. Device deficiencies are only applicable to the WavelinQTM EndoAVF System. All device deficiencies will be recorded on the appropriate eCRF page and be promptly reported to the Sponsor. The device(s) should be returned to the Sponsor as outlined in the investigational site's regulatory binder. The site may also be contacted to provide additional information to allow the Sponsor to conduct a thorough investigation. This applies to:

• WavelinQTM EndoAVF Systems used in the participant; or

- WavelinQTM EndoAVF Systems in which the package was opened, but the device was not used; or
- WavelinQTM EndoAVF Systems with which insertion attempts were made, but the WavelinQTM EndoAVF System was not used in the participant.

If the device deficiency was associated with an AE, the reporting provisions for AEs, ADEs, SAEs, SADEs and UADEs / USADEs apply (see Section 8.4 and 12.4). Any device deficiency that did not lead to an AE but could have led to a SADE, if suitable action had not been taken, if intervention had not been made or if circumstances had been less fortunate must be reported to the Sponsor within one (1) working day of the event (see Section 12.4). It is the responsibility of the PI to notify the IRB / EC of such device deficiencies as, and if, applicable in accordance with the IRB / EC requirements and / or the Regulatory Authority's local regulations.

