7.2 Analysis Populations

The analysis populations will be defined as follows:

- The ITT population will consist of all participants into whom the WavelinQTM Endovascular System was introduced including those in whom procedure success was not achieved.
- An As-Treated (AT) population will include all treated participants, which includes all ITT participants but excludes those into whom the WavelinQTM Endovascular System was introduced but procedure success was not achieved.
 - The AT population is composed of two subpopulations: The incident population and the prevalent population as defined in Section 4.5.2.
- A Per-Protocol (PP) population may be created if there are participants who have any major deviations. The PP population will consist of any participants in the AT population who do not have any major deviations. The deviations that are considered to have a "major" grade will be defined a priori in the SAP.

All effectiveness endpoints will be analyzed primarily based on the AT population. All safety endpoints will be analyzed primarily based on the ITT population. PP analyses may also be performed for the primary endpoints. They will only serve as sensitivity analyses for the primary analyses.

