## 4 Analysis Population Set(s)

## 4.1 Population Definitions

The analysis populations will be defined as follows:

- The Intent-to-Treat (ITT) population will consist of all participants into whom the WavelinQTM Endovascular System was introduced including those in whom procedure success was not achieved.
- An As-Treated (AT) population will include all treated participants, which includes all ITT participants but excludes those into whom the WavelinQTM Endovascular System was introduced but procedure success was not achieved. The AT population is composed of two subpopulations:
  - o Incident population: Participants who have not previously and who were not actively receiving HD prior to or at the time of the index procedure but are in need of a vascular access as determined by the referring clinician. This subgroup population will be identified if the question of "Has the Subject had any Kidney Replacement Therapy (KRT) up until time of Index Procedure (Kidney Transplant, Peritoneal Dialysis and/or Hemodialysis)?" on the Dialysis History/Onset page is answered as No, or if the question is answered as Yes but "Hemodialysis" is not selected.
  - O Prevalent population: Participants who have previously and/or who were actively receiving HD prior to the index procedure. This subgroup population will be identified if the question of "Has the Subject had any Kidney Replacement Therapy (KRT) up until time of Index Procedure (Kidney Transplant, Peritoneal Dialysis and/or Hemodialysis)?" on the Dialysis History/Onset page is answered as Yes and "Hemodialysis" is selected.
- A Per-Protocol (PP) population may be created if there are participants who have any major deviations. The PP population will consist of any participants in the AT population who do not have any major deviations. The deviations that are considered to have a "major" grade will be defined a priori in the SAP.

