### 6.10 Device Failure, Malfunctions and Defects

Device deficiencies/malfunctions will be tabulated by the failure code. This summary will be reported based on the ITT population.

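### The SAP's device-deficiency table is limited to ITT, so a recorded deficiency is left out when no system was ever introduced into the participant

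*Protocol*

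**What the plan says.** Protocol 8.6 sets a broad recording duty: "All device deficiencies will be recorded on the appropriate eCRF page and be promptly reported to the Sponsor". It applies this to three classes of system: those used in the participant, those "in which the package was opened, but the device was not used", and those "with which insertion attempts were made, but the WavelinQTM EndoAVF System was not used in the participant".

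SAP 6.10 sets a narrower reporting rule: "Device deficiencies/malfunctions will be tabulated by the failure code. This summary will be reported based on the ITT population".

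Protocol 7.2 defines that population: "The ITT population will consist of all participants into whom the WavelinQTM Endovascular System was introduced". The definition goes on to include participants without procedure success. SAP 4.1 matches it, and the shorter ITT entry in protocol Appendix B also depends on introduction of the system.

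Under protocol 6.2.1, a participant into whom no system was introduced leaves the investigation at the index procedure, with the reason noted on an eCRF.

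**The concern.** The recording rule and the reporting rule have different scopes, and the difference is not neutral. Entry to the ITT population depends on a system being introduced, and some deficiencies can prevent exactly that. A defect found on opening the package, with no second system introduced, both creates a reportable deficiency and removes the participant from the set in which deficiencies are tabulated. For that class, the exclusion depends on the outcome being counted.

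At stake is the completeness of a descriptive device-reliability table in a post-market investigation meant to add to the evidence on safety and effectiveness. A reader of the report would probably take the table as the full count of deficiencies seen in the investigation.

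**Working it through.** There is no planned figure to reproduce and no arithmetic on sample size, power or alpha. The check compares the scope of protocol 8.6 with that of SAP 6.10. It reads the ITT restriction as a filter on participants, so every deficiency attached to an ITT participant is tabulated.

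| Situation | Within protocol 8.6? | Participant in ITT? | In the SAP 6.10 table? |
|---|---|---|---|
| System introduced, deficiency found, any procedural outcome | Yes | Yes | Yes |
| First system opened and not used; a replacement introduced, successfully or not | Yes | Yes | Yes |
| Insertion attempted, system not used, no other system introduced | Yes | Unclear: neither document defines introduced | Unclear |
| System opened and not used, no other system introduced | Yes | No | No |

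The last row is the definite gap and the third is a possible one.

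The next step is whether other output in the SAP text recovers the last row:

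- SAP 5.3.1 (procedure success) is evaluated on ITT, so it has the same filter.
- SAP 6.1 (disposition) counts participants in whom the device was inserted without treatment, but names no category for a system opened and never introduced. Its breakdown of discontinuations by reason might show such a participant indirectly, but not the deficiency or its failure code.
- Screen failures are defined in protocol 5.3 by the eligibility criteria, so an eligible participant whose device failed before entry is not one.
- SAP 7.1 provides listings of AEs, SAEs and UADEs. A deficiency with no associated event appears in none of them.

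On size, let k be the deficiencies recorded in ITT participants and m those recorded in participants with no system introduced. The share missing from the table is m / (k + m). The documents give neither k nor m. If m = 0 the share is 0; otherwise it cannot be computed.

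One further passage bears on the comparison. The opening of protocol Section 8, which contains 8.6, says events are collected for ITT participants from the initial skin puncture. If events there include deficiencies, the protocol is inconsistent with itself: 8.6 covers a package opened without any system being introduced, and the Section 8 opening would not.

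**The case against.** The strongest reply is that this is a narrow gap in a descriptive table. No endpoint or hypothesis test uses it. Recording on the eCRF and reporting to the Sponsor under protocol 8.6 do not depend on the analysis population. If the opening of Section 8 governs, SAP 6.10 simply follows the protocol. The table shells in SAP Appendices 1.1 and 1.2 are named but their content is not available here, so a listing of all deficiencies may already be planned. All of this stands as a limit on the point, but none of it brings the two scopes into line.

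A reader might also infer more than the documents support:

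- That only deficiencies followed by a successful replacement survive. Procedure success is not a condition of ITT. Every deficiency of an introduced system stays, as does any followed by introduction of a replacement.
- That all failed insertion attempts drop out. Because introduced is undefined, a partial insertion might count as introduction.
- That this table is the trial's only statement on device reliability. Procedure success also bears on reliability, and the formal safety claim rests on the 30-day freedom from device- or procedure-related SAEs.
- That near misses would go unreported. Protocol 8.6 and 12.4 require those with potential for a serious adverse device effect to reach the Sponsor within one working day, whatever the analysis population.
- That a sizeable share of deficiencies is lost. Any percentage would rest on assumed counts.

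**Conclusion.** The mismatch is real but narrow. A deficiency recorded under protocol 8.6 in a participant into whom no system was ever introduced falls outside the only deficiency summary in the SAP text. This is clear for systems opened but not used with no replacement introduced, and uncertain for failed insertion attempts. The number affected cannot be derived from the documents and may be zero. The two co-primary endpoints, their power and expedited reporting are unaffected.

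The conclusion assumes that the ITT restriction works at participant level, that 8.6 applies as written despite the opening of Section 8, and that the unseen table shells do not already add the missing cases. The correction is worth making because it is cheap and removes an exclusion that depends on the outcome being reported.

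**What to change.** In SAP 6.10, replace the ITT restriction with all deficiencies recorded under protocol 8.6 in any enrolled participant, tabulated by failure code. Keep the ITT count as a sub-row and show the non-ITT deficiencies separately, as a count or a listing. Use the number of systems opened as a denominator only if that number is captured; neither document shows that it is.

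In the protocol, reconcile the opening of Section 8 with 8.6, so that sites know whether deficiencies are to be recorded for participants outside ITT and before skin puncture.

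The cost is a change of SAP wording, one revised table shell and a clarifying protocol edit. If 8.6 governs, the data are already required on the eCRF. The downside is a possibly slightly higher reported deficiency count.

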8.7 Serious Health Threat

A serious health threat is a signal from any AE or device deficiency that indicates an imminent risk of death or a serious deterioration in the health in participants, users or other persons, and that requires prompt remedial action for other participants, users or other persons. This would include events that are of significant and unexpected nature such that they become alarming as a potential serious health hazard or possibility of multiple deaths occurring at short intervals. Serious health threats will be reported as per IRB / EC and regulatory requirements, if applicable.

8.8 Safety Committees

8.8.1 Medical Monitor

The Medical Monitor (MM) will be responsible for AE trending review as well as for the identification of signals that could indicate a serious health threat as specified in the Safety Management Plan.

8.8.2 Clinical Events Committee (CEC)

The CEC will be comprised of at least two (2) members (interventional radiologists, non-interventional / interventional nephrologists, or surgeons) who are not directly involved in the conduct of this clinical investigation. The CEC is responsible for the development of specific criteria used for the categorization of clinical events and clinical endpoints in the clinical investigation as determined by the CEC charter. The CEC will meet regularly to review and adjudicate all AEs defined in the charter. The CEC will have access to the eCRF associated with the reported AE for each participant. The Sponsor will forward all associated relevant de-identified documents (i.e., physician notes, operative reports, imaging, etc.) to the CEC upon request. The CEC will forward an adjudication report of AEs to the Sponsor in a timely fashion. Minutes

of all meetings will be recorded and distibuted as appropriate. The Sponsor will ensure that if applicable, appropriate information is provided to the Regulatory Authorities, the PIs, and all reviewing IRB / ECs.

9 RISK / BENEFIT ANALYSIS

9.1 Risk Assessment

The known possible risks associated with the use of the WavelinQ™ EndoAVF System are listed below and have been made available to the PI(s) in the IFU. Complications that may be associated with AEs, medical intervention and / or death that could occur with use of the WavelinQ™ EndoAVF System may include:

- aborted or longer procedure;
- additional procedures;
- bleeding, hematoma or hemorrhage;
- bruising;
- burns;
- death;
- electrocution;
- embolism;
- failure to mature;
- fever:
- increased risk of congestive heart failure;
- infection;
- numbness, tingling, and / or coolness;

- occlusion / stenosis;
- problems due to sedation or anesthesia;
- pseudoaneurysm;
- aneurysm;
- sepsis;
- steal syndrome or ischemia;
- swelling, irritation, or pain;
- thrombosis;
- toxic or allergic reaction;
- venous hypertension (arm swelling);
- vessel, nerve, or AVF damage or rupture;
- wound problem

The risks associated with use of the WavelinQTM EndoAVF System have been identified by performing a Use Failure Mode and Effects Analysis as well as a Design Failure Mode and Effects Analysis (UFMEA and DFMEA) on the system and its use. The Sponsor also conducted non-clinical testing as well as clinical investigations to confirm that the WavelinQTM EndoAVF System has element safety and effectiveness to create endoAVFs. A Risk-Benefit Analysis (RBA) was then subsequently performed. At the completion of the UFMEA, DFMEA and RBA, a Risk Management Report was generated to summarize the risk analysis process and provide documented evidence that all individual and cumulative risks associated with the use of the WavelinQTM EndoAVF System have been adequately managed and reduced as low as possible. Any residual risks identified with the investigation intervention that are identified in the device RBA are also captured and tracked along with their mitigation strategies for this investigation using the investigation's Risk Analysis. Risks identified for associated / concomitant procedures are identified in Table 3 alongside their mitigation strategies.

Table 3: Risk Assessment

Potential Risk of Clinical Significance	Summary of Risk	Mitigation Strategy			
Associated / Concomitant Procedures					
Risks associated with sedation and / or anesthesia	These risks can include: Nausea Vomiting Hematoma at injection site Sore throat / hoarse voice Damage to teeth Brain damage Death These risks can include:	 As delineated in Section 12.1 the PI as well as any additional operators (as applicable) must be experienced in the field of application. Clinical Eligibility Criteria must be met and documented using prior to treatment including assessment of the participants eligibility to receive sedation and / or anesthesia (Section 5.1). The CIP required follow-up ensures close participant monitoring for AEs throughout the course of the investigation (Section 6.4). As delineated in Section 12.1 the PI 			
angiography	Kidney damage Allergic reaction	 as well as any additional operators (as applicable) must be experienced in the field of application. Clinical Eligibility Criteria must be met and documented using prior to treatment including assessment of the participants eligibility to receive contrast media (Section 5.1). The CIP required follow-up ensures close participant monitoring for AEs throughout the course of the investigation (Section 6.4). 			
Risks associated with vessel embolization placement, if completed.	These risks can include: Allergic reaction Hemolysis Migration Occlusion of unintended vessel Recanalization Stroke Tissue ischemia Vessel trauma including perforation, rupture, or extravasation Others, as delineated in the embolization device labeling and IFU	 As delineated in Section 12.1 the PI as well as any additional operators (as applicable) must be experienced in the field of application. The CIP required follow-up ensures close participant monitoring for AEs throughout the course of the investigation (Section 6.4). 			

